9.4.15 Initiation of intervention

The investigator will hand over the study medication batch 1 to the respective prover as per their allotted codes. Each prover will be instructed to:

- Take 4 doses in a day (4 hourly) for 3 days. The number of pills to be taken must be explained properly to the prover.
- The study medication is to be taken dry on tongue
- Record the date and time of intake and of number of doses taken in the Form E
- Take detailed notes daily regarding his/her feelings/changes in mind and body after taking the study medication, in the 'Form E'.
- In case is no symptoms appear, the prover is requested to note down the date and time of intake of the respective dose of the drug and mention 'no symptoms' in the form E.
- The prover must follow the instructions in the participant information sheet and those given by the investigator from time to time.
- The prover must inform the site investigator if any symptoms/signs appear or he/she feels there is a change in the health status. If so, Prover must stop the intake of further doses as directed by the site investigator.

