9.4.12 Dosage schedule

Each batch will have 12 doses. The provers will be instructed to take 4 pills, 4 times a day at four hourly interval for 3 days.

In case of drugs which the Council proposes to re-prove considering that the previous proving has generated very few symptoms, the following dosage schedule is proposed:

Day	Number of pills*	Number of doses
1	4	4 times
2	8	4 times
3	12	4 times

* the number of pills taken on each day will be increased consecutively in concordance with the Organon of medicine (Aphorism 129), where in it is mentioned that “a few more globules may be taken”^[6]

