9.4.16 Data Recording

The prover will be expected to make a daily record of the date and time of intake of study medication in the prescribed proforma. During the 3 day study medication intake period, the prover will report to the investigator daily. The investigator will interrogate the prover about the change in health status/sign and symptoms if any during this period and will record his/her observations in the symptom elaboration proforma (**Form F & G**).

Each symptom must be completed with respect to order of appearance, time of appearance & disappearance, location, sensation/character, modalities, concomitants, direction/extension of symptoms, etc. Clinical examination findings will also be recorded. Appropriate pathological investigations if required would also be advised and the report will be added. For each symptom, the investigator on detailed interrogation with the prover, will classify and mention their symptoms as follows^[9]:

- **NS** - New symptoms, not previously experienced.
- **C-** - Unexpected change representing worsening or aggravation of ongoing or recurring symptoms.
- **C+** - Unexpected change representing an improvement of ongoing or recurring symptoms.
- **RS** - Unexpected recurrence of past symptoms.

The investigator will also record his/her observation about the possible causality of symptoms with the drug intake.

9.4.17 Follow up:

A. If sign(s)/symptoms(s) appear:

- The prover must stop taking the further dose of study medication as soon as he/she feels any change in health status or any sign(s) &/or symptoms(s) develop in accordance with the qualifiers of proving symptoms as described in section 13.2. The investigator will ascertain the qualifiers of the symptom and will advise the prover to stop intake of further doses, once proving symptoms develop.
- The prover notes down the sequence of the appearance of new sign(s) &/or symptoms(s), their progress and the number of doses after which each sign &/or symptom appears with date, time of onset and duration for which it persists. No further dose of the same batch is to be consumed by the prover.
- The prover is expected to report (preferably on a personal visit or telephonically) to the investigator daily (or more frequently) for as long as the symptoms persist.

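### Sections 9.4.15 and 9.4.17 A disagree on who stops a batch and on what trigger, so the doses received can depend on site practice

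*Protocol*

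**What the plan says.** Protocol 9.4.15 lists what each prover is told when a batch is handed over. The last item requires the prover to inform the site investigator of any symptom, sign or felt change, and then: "If so, Prover must stop the intake of further doses as directed by the site investigator".

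Protocol 9.4.17 A (follow-up when symptoms appear) opens differently: "The prover must stop taking the further dose of study medication as soon as he/she feels any change in health status". The same sentence adds a second limb, for signs or symptoms that "develop in accordance with the qualifiers of proving symptoms as described in section 13.2". The sentence after it reads: "The investigator will ascertain the qualifiers of the symptom and will advise the prover to stop intake of further doses, once proving symptoms develop". The next bullet makes the stop final: "No further dose of the same batch is to be consumed by the prover".

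Three other places bear on the point:

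- Section 9.4.12 sets the exposure ("Each batch will have 12 doses", four a day at four-hour intervals for three days).
- Section 9.4.16 sets the contact schedule: "During the 3 day study medication intake period, the prover will report to the investigator daily".
- Sections 9.4.17 A and 13.4 both collect the number of doses taken before each symptom appeared.

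**The concern.** The three statements name two decision-makers and at least two triggers. In one, the prover acts alone and at once. In the others, the investigator directs or advises, and the last of them waits until a proving symptom has been established. A site that trains its provers on 9.4.15 and a site that trains them on the first sentence of 9.4.17 A can give different numbers of doses to provers with the same experience.

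Exposure to each potency is the treatment in this trial. The plan also uses repeated exposure when it reads the results: 14.1.1 counts repeated occurrence shortly after administration as evidence that a symptom belongs to the drug, and 15.3 weighs consistency and increase over repeated doses when judging the causality of adverse events. What can be seen on those criteria depends on whether dosing went on after the first change. If site habit settles that, part of the difference between centres has nothing to do with the substance.

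**Working it through.** No sample size, power or error rate is involved. The check sets the wording side by side and then counts doses.

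**1. The three statements**

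| Place | Who stops the batch | Trigger |
|---|---|---|
| 9.4.15, last instruction | Site investigator directs, once informed | Any symptom, sign or felt change is reported; no criterion is given for the direction |
| 9.4.17 A, first sentence | Prover, at once | Felt change, or signs/symptoms meeting 13.2; unclear whether the qualifier also limits the felt change |
| 9.4.17 A, second sentence | Investigator advises | Proving symptom, after the qualifiers are checked |

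The triggers are not equivalent. Section 13.2 excludes symptoms in line with the prover's historical tendency and those confidently put down to an outside cause, so a felt change need not be a proving symptom. Form F gives the classification to the investigator, after full questioning and with the pre-trial and run-in records in view.

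**2. Doses received when the change does qualify**

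Plan's own figure: 4 doses a day × 3 days = 12, which matches 9.4.12.

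Let the change appear after dose k.

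- Prover stops at once: doses received = k.
- Stop waits for the next daily report: doses received = k + e, where e is the number of doses due before that report, limited to 12 − k.

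Values of e for k = 1 to 11, by when in the day the report falls:

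| Daily report falls after | e for k = 1, …, 11 | Maximum | Mean |
|---|---|---|---|
| the day's dose 4 | 3, 2, 1, 4, 3, 2, 1, 4, 3, 2, 1 | 4 | 26/11 = 2.36 |
| the day's dose 1 | 4, 3, 2, 1, 4, 3, 2, 1, 3, 2, 1 | 4 | 26/11 = 2.36 |
| the day's dose 2 | 1, 4, 3, 2, 1, 4, 3, 2, 1, 2, 1 | 4 | 24/11 = 2.18 |
| the day's dose 3 | 2, 1, 4, 3, 2, 1, 4, 3, 2, 1, 1 | 4 | 24/11 = 2.18 |

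The means assume that onset is equally likely after each of doses 1 to 11; the protocol gives no onset distribution. The maximum is 4/12 = 33% of the batch. If the prover telephones at once, e = 0. Section 9.4.15 sets no time limit for informing the investigator, so the text allows 0 to 4.

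Under the re-proving schedule in 9.4.12, the pills are 4×4 + 8×4 + 12×4 = 16 + 32 + 48 = 96. If onset follows dose 8 and the report falls after the day's last dose, the four extra doses are 48 pills, or 48/96 = 50% of the batch.

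**3. Doses received when the change does not qualify**

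If the prover stops on any felt change, the batch ends at k. If only a confirmed proving symptom stops it, dosing may go on to 12. The remaining 12 − k doses then depend on the reading, and the batch has ended for something that 13.2 excludes.

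**4. The recorded dose count at onset**

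- First recorded symptom: k on either reading, because it is fixed before any stop rule acts.
- Later symptom in the same batch: at most k if the prover stops at once, up to k + 4 if the stop waits for the daily report.
- First qualifying symptom after a non-qualifying change: at most k on one reading, up to 12 on the other.

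**The case against.** The best reply is that the passages form one sequence: the prover holds dosing and reports, and the investigator then checks and confirms. Nothing in the text forbids this, and on that reading the qualifier in 9.4.17 A may govern the whole sentence, leaving one trigger. The reply shows that a reconciliation is possible, but the protocol does not write it. The text has no hold step and no rule for restarting after a hold, and it rules out further doses from the batch.

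It is also fair that four doses is the upper limit. No passage tells a prover to keep dosing until the daily report, 9.4.15 asks for reporting when symptoms appear, and Form F has a log for telephone reports. That is why the size is a range starting at zero.

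A reader might infer more than the documents support:

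- *That dose-to-onset data are unreliable in general.* The count for the first symptom does not move, and neither incidence measure in 14.2 uses it.
- *That Grade I status turns on the stopping rule because it needs agreement between sites.* Two-site agreement is one of three listed routes in 14.1.3, and symptom recording continues after a stop, through observation and washout.
- *That some stated share of batches will be cut short.* That needs a background rate of felt changes and the fraction meeting 13.2. The protocol gives neither, and any figure would only reflect what was assumed.
- *That the arms are treated differently.* Provers and site investigators are blind to allocation (9.4.8), so a site's habit is not knowingly applied by arm. The problem is uneven exposure between sites.

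**Conclusion.** The contradiction stands, between 9.4.15 and 9.4.17 A and within 9.4.17 A itself, on both the decision-maker and the trigger. For a qualifying change the resulting difference is 0 to 4 of 12 doses, depending only on how quickly the investigator is reached. For a non-qualifying change, the rest of the batch may be lost on one reading and not on the other. Dose counts can be affected only for later symptoms in a batch or for a first qualifying symptom after a non-qualifying change.

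The range of 0 to 4 rests on the stated schedule and contact frequency alone; only the averages of about 2.2 to 2.4 doses need an assumption about onset. How often sites would diverge cannot be estimated from the protocol. It should be corrected because the document is a generic protocol, and each proving that uses it inherits the ambiguity.

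**What to change.** The sponsor should reconcile 9.4.15 and both sentences of 9.4.17 A to one trigger and one decision-maker, make clear what the 13.2 qualifier applies to, and use identical wording in the prover instructions. Which rule to adopt is a clinical decision, and no view is given here.

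Add two fields to Form E: who decided to stop the batch, and the reason. The last dose taken needs no new field, because Form E Part 2 already has a row for each dose with its date and time, and 9.6 provides a pill count as a cross-check.

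In the compilation under 13.4, report doses taken per batch by arm and centre, and keep batches stopped for a change later excluded under 13.2 identifiable.

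The cost is a wording amendment, two form fields and one table. Enrolment, visits and sample size do not change.

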9.4.16 Data Recording

The prover will be expected to make a daily record of the date and time of intake of study medication in the prescribed proforma. During the 3 day study medication intake period, the prover will report to the investigator daily. The investigator will interrogate the prover about the change in health status/sign and symptoms if any during this period and will record his/her observations in the symptom elaboration proforma (**Form F & G**).

Each symptom must be completed with respect to order of appearance, time of appearance & disappearance, location, sensation/character, modalities, concomitants, direction/extension of symptoms, etc. Clinical examination findings will also be recorded. Appropriate pathological investigations if required would also be advised and the report will be added. For each symptom, the investigator on detailed interrogation with the prover, will classify and mention their symptoms as follows^[9]:

- **NS** - New symptoms, not previously experienced.
- **C-** - Unexpected change representing worsening or aggravation of ongoing or recurring symptoms.
- **C+** - Unexpected change representing an improvement of ongoing or recurring symptoms.
- **RS** - Unexpected recurrence of past symptoms.

The investigator will also record his/her observation about the possible causality of symptoms with the drug intake.

9.4.17 Follow up:

A. If sign(s)/symptoms(s) appear:

- The prover must stop taking the further dose of study medication as soon as he/she feels any change in health status or any sign(s) &/or symptoms(s) develop in accordance with the qualifiers of proving symptoms as described in section 13.2. The investigator will ascertain the qualifiers of the symptom and will advise the prover to stop intake of further doses, once proving symptoms develop.
- The prover notes down the sequence of the appearance of new sign(s) &/or symptoms(s), their progress and the number of doses after which each sign &/or symptom appears with date, time of onset and duration for which it persists. No further dose of the same batch is to be consumed by the prover.
- The prover is expected to report (preferably on a personal visit or telephonically) to the investigator daily (or more frequently) for as long as the symptoms persist.
- Since the symptoms appearing during proving are transient in nature, it is not expected that the symptoms will persist for long. During the course of proving, the prover is referred to medical expert/consultant for examination & for specific laboratory investigation(s), if needed, to rule out any pathological cause for appearance of new symptom(s)/sign(s) in case symptoms persist for more than 3 days or is distressing to the prover. Laboratory tests are also performed to facilitate observation of any correlation between the subjective and objective changes during the course of proving. The opinion of the experts is also taken, on the appearance of new sign(s)/symptom(s), wherever needed.
- Photos of objective findings (e.g. skin eruptions, swellings, etc.) will also be taken and to be kept along with the prover record.

Observation period: During the period that the symptoms persist, the prover will be kept under observation of the investigator. The prover will be instructed to report (preferably on a personal visit or telephonically) to the investigator daily (or more frequently) for as long as the symptoms persist.

Washout period: Subsequent to disappearance of the symptoms, a period of 30 days will be kept as washout period. The prover will report to the investigator once a week (or earlier in case of

development of any symptoms or any change in health status) during which the investigator will interrogate and examine the prover to identify any change in health status. The prover (in form E) and the investigator (in form F&G) will be expected to complete the details of the symptoms as mentioned in section 9.4.16.

In case of appearance of symptoms during this period, the prover will be kept under observation of the investigator. The prover will be instructed to report (preferably on a personal visit or telephonically) to the investigator daily (or more frequently) for as long as the symptoms persist. After symptoms have disappeared, a period of further 30 days symptom free period will be maintained as a wash out period before the start of the next batch of study medication.

B. If no sign(s)/symptoms(s) appear:

Prover may not develop any sign/symptom till the completion of 12 doses. In such a case, the prover notes down as 'No Symptom' with date and time of intake of the respective dose of the drug, verified by the investigator.

Washout period: In such a case, a wash out period of 30 days will be maintained after the last dose of the IP/placebo from the batch has been taken. During this period, the prover will be expected to keep a daily record of his/her health status. The prover will report to the investigator once a week (or earlier in case of development of any symptoms or any change in health status) during which the investigator will interrogate and examine the prover to identify any change in health status. The prover will be expected to record the details of the symptoms as mentioned in 9.4.16 and the investigator is also expected to complete the symptom details as outlined in the same section.

9.4.18 The same procedure is followed till all the batches of the study medication are consumed.

9.4.19 Post –Trial (Terminal) Medical examination (Form D)

After all the batches of the study medication are consumed and a subsequent washout period of 30 days, the provers are examined again as in the PME, and the process is called 'Terminal Medical Examination' (TME). The TME must be completed within two weeks after completion of the washout period.

9.5 Dietary & lifestyle guidelines for Provers

Prover will be instructed to follow his/her normal daily routine and dietary habits till the time he/she is enrolled in proving.

9.6 Steps to maximize adherence & retention

All the provers shall be motivated to adhere to study schedule and for measurement of various investigations from time to time by the investigator. Provers are instructed to return the glass containers with their study medication, and a pill count will take place (or the absence of pills will be confirmed if the subject reports that the full batch was taken).

10. When and how to withdraw the provers

It is the responsibility of the site investigator to maintain the prover in the study, provided it is safe to do so. A prover may be discontinued from the study in case of occurrence of serious adverse event(s) or serious inter-current illness or for any of the following reasons, which must be documented in the TME form. The prover who withdraws from the study will be requested to undergo a complete terminal medical examination if possible, or if leaves against advice of site investigator will at least be requested for a final telephonic interview at the same time with regard to the state of prover's health.

Discontinuation of Provers

The prover will be discontinued from proving, and prover will be withdrawn early if

- 1) Non-compliance to proving protocol
- 2) Prover withdraws consent
- 3) Discretion of the investigator(s)

10.1 Data collection and follow up for withdrawn subjects

The data will be collected which includes PME/TME information, prover symptoms, symptom elaboration, clinical and laboratory findings, etc. till the prover is in the study trial. Such data is important to the integrity of the final study analysis since withdrawal could be related to the safety profile of the IPS.

11. STUDY DURATION

The duration of proving for each prover will depend upon the symptoms produced and the subsequent wash out periods, needed, before subsequent doses can be given.

Expected duration for study

11.1 At research centre level:

- Prover screening: 1 week
- PME: 2 weeks (for completion of PME at a centre)
- Run in period (till receipt of IP batches): 2 weeks (to a maximum of 4 weeks)
- Administration of first batch: 3 days
- First washout period: 30 days (+ days for which symptoms persisted)
- Administration of second batch: 3 days
- Second washout period: 30 days (+ days for which symptoms persisted)
- Administration of third batch: 3 days
- Third washout period: 30 days (+ days for which symptoms persisted)
- TME: 1 week (to 2 weeks for completion of PME at a centre)

[figure not shown]
In case where no symptoms appear, a symptom free period of 30 days is maintained. In case(s) where symptoms appear, the observation period for each prover will vary depending on the duration for which the proving symptoms persist, subsequently followed by a 30 day symptom free washout period. (See section 9.4.17 for details)

As such for proving of each IPS an approximate duration of 7 months to 12 months is needed.

11.2 At Headquarters level, the study duration will include:

- Protocol preparation, regulatory approval, pretrial preparations: 2 months
- PME Assessment, randomization and allotment of batches, preparation of batches: 2 weeks (to a maximum of 3 weeks)
- Monitoring and supervision of study at research centre level: 7 months (to approx. 12 months)
- Data compilation & de-coding & analysis: 2 months
- Report preparation: 1 month

11.3 Flow chart for proving cycle and study process

12. PROVER PARTICIPATION TIMELINE

[figure not shown]
Day/ Month	0 day	Day 1-7	2 wee ks	Day 1-3 (batc h 1)	no. of days for which symp toms persist	30 days	Day 1-3 (Batc h 2)	no. of days for which symp tom persist	30 da ys	Day 1-3 (Bat ch 3)	no. of days for which symp tom persist	30 da ys	1 week
Screening (Form A)	√												
Informed consent (Form B1 & B2)	√												
PME (History & General Examination) (Form D)		√											
Photograph		√											
Enrollment of prover			√										
Allocation of subject number at CCRH			√										
Run in period			√										
Intervention				√			√			√			
Face to face interview	√	√		√	√		√	√		√	√		√
Telephonic interaction													
Observation period					√			√			√		
Prover daily diary completion (Form E)			√	√	√	√	√	√	√	√	√	√	
Symptom elaboration proforma (Form F)			√	√	√	√	√	√	√	√	√	√	
Washout period						√			√			√	
TME (Form D)													√
AE/SAE assessment (Form G)				√	√	√	√	√	√	√	√	√	√

13. DATA COLLECTION AND MANAGEMENT

Data compilation and analysis by the proving team is a key factor in the translation of raw Proving data into a meaningful clinical drug picture that can be used by a prescriber. The data analysis process must be carefully designed to avoid excessive inclusion of non-specific, non-characteristic data, yet ensure that the most characteristic and dependable data for homeopathic prescribing is maintained. An analysis process to extract dependable homeopathic prescribing indications from a drug Proving is required to contain the following dimensions (as described in information that follows) [9]:

- 1st dimension: All symptoms occurring during the Proving
- 2nd dimension: Proving symptoms with relative characterizing assessment
- 3rd dimension: Characteristic symptoms (a highly individualized subset)[8]

Figure 1 Dimension of symptoms occurring during proving

Data will be recorded on pre-designed formats & managed on MS Excel spreadsheet at each of the study center. The study site investigators will send periodic updates at end of each stage i.e. PME, completion of each batch of drug and subsequent observation & wash out period and TME. Time line & assessment schedules shall be strictly maintained and recorded in the prescribed formats.

